## 5.1 Screening/Enrollment period

All screening and enrollment procedures will be performed according to the assessment schedules in Table 2. Demographic data and other characteristics will be recorded including date of birth, gender and smoking history, etc, according to local regulations. A standard medical and surgical history will be obtained.

Written informed consent and any locally required privacy act document authorization must be obtained prior to performing any protocol-specific procedures, including screening evaluations. If laboratory or imaging assessments were performed for alternate reasons prior to signing consent, these can be used for screening purposes with consent of the patient.

Screening and baseline evaluations may be performed over more than 1 visit if required.

## 5.2 Treatment period

All procedures to be conducted during the treatment period will be performed according to the assessment schedule (see Table 2).

Whenever vital signs, electrocardiograms (ECGs), and blood draws are scheduled for the same nominal time, the assessments should occur in the following order: ECG, vital signs and then blood draws.

## 5.3 Follow-up period

Patients who are permanently discontinued from further receipt of IP, regardless of the reason, will be identified as having permanently discontinued treatment and will enter follow-up.

Patients who permanently discontinue drug for reasons other than objective disease

progression should continue to have tumor assessment until disease progression as per investigator assessment.

All patients will be followed for survival until the end of the study.

## **6 STUDY ASSESSMENTS**

The investigator will ensure that data are recorded on the eCRFs as specified in this study protocol and in accordance with the instructions provided.

The investigator ensures the accuracy, completeness, and timeliness of the data recorded and the provision of answers to data queries according to the clinical study agreement (CSA). The investigator will sign the completed eCRFs. A copy of the completed eCRFs will be archived at the study site.

### **6.1 Efficacy assessments**

This study will evaluate the efficacy of durvalumab + EP as secondary endpoints, in terms of OS, as well as PFS, APF12, ORR, and DoR, which will be derived from site Investigator assessments per RECIST1.1.

Tumor assessments should utilize images from CT (preferred) or MRI, each preferably with IV contrast, of the chest and abdomen (including the entire liver and both adrenal glands), collected during screening/baseline and at regular (follow-up) intervals during study treatment. Any other areas of disease involvement should be additionally imaged based on the signs and symptoms of individual patients. It is important to follow the tumor assessment schedule as closely as possible (refer to the SoA, Table 2). Treatment continues until clinical progression/deterioration or confirmed radiological progression (refer to Section 8.2.1), and scanning/tumor assessments should continue throughout treatment until RECIST 1.1-defined radiological progression plus an additional follow-up scan (if clinically feasible).

The RECIST 1.1 guidelines (Appendix C) provide a method of assessment of change in tumor burden in response to treatment. Screening/Baseline imaging should be performed no more than 28 days before start of study treatment, and ideally should be performed as close as possible to and prior to the start of study treatment. The RECIST 1.1 assessments of baseline images identify Target Lesions (TLs) (defined as measurable) and Non-Target Lesions (NLTs). On-study images are evaluated for TLs and NLTs chosen at baseline, and for New Lesions (NLs) when they appear. This allows determination of follow-up TL response, NTL lesion response, the presence of unequivocal NLs, and overall timepoint responses (CR, PR, SD, PD, or Not Evaluable [NE]).

The date, procedure, and overall response should be documented at each follow-up visit timepoint as well as if the patient is taking benefit from the study medication. In case of disease progression, the physician will assess, date, and document the progression and methods (eg CT scan) used as per standard definitions and routine institutional standard of care.

## 6.2 Survival assessments

The survival status of the patient will be collected during the study. After discontinuation of study treatment, patients will continue to be followed for survival via phone calls or email every 3 months to study end. The survival status (including cause of death) and the date of death or last follow-up date will be collected.

## 6.3 Safety assessments

### 6.3.1 Clinical safety laboratory assessments

Blood and urine samples for determination of clinical chemistry, hematology, and urinalysis will be taken at the times indicated in the assessment schedules and as clinically indicated. Clinical laboratory safety tests, will be performed in a licensed clinical laboratory according to local standard procedures. Urine pregnancy tests may be performed at the site using a licensed test (urine or serum pregnancy test). Abnormal clinically significant laboratory results should be repeated as soon as possible (preferably within 24 to 48 hours).

Additional safety samples may be collected if clinically indicated at the discretion of the Investigator and according to standard medical practice. The date, time of collection, and results (values, units, and reference ranges) will be recorded. The Investigator should make an assessment of the available results with regard to clinically relevant abnormalities. The laboratory results should be signed and dated and retained at center as source data for laboratory variables. For information on how AEs based on laboratory tests should be recorded and reported, see Section 7.3.6.

Other safety tests to be performed at screening include assessment for hepatitis B surface antigen, hepatitis C antibodies and HIV antibodies. T-spot TB test will be performed when determined to be essential by investigator.

Sample tubes and sample sizes may vary depending on laboratory method used and routine practice at the site. Clinically significant (as assessed by the Investigator) laboratory abnormalities will be recorded as AEs. Laboratory results relevant to / associated with imAE will be recorded.

The laboratory variables to be measured are presented in Table 3 (clinical chemistry), Table 4 (hematology), and Table 5 (urinalysis).

**Table 3 Clinical chemistry**

---

|                      |                              |
|----------------------|------------------------------|
| Albumin              | Lipase b          |
| Alkaline phosphatase | Magnesium c       |
| ALT a     | Potassium                    |
| Amylase b | Sodium                       |
| AST a     | Total bilirubin a |

|  |  |
|--|--|
| Bicarbonate c               | Total protein  |
| Calcium                                | TSH e   |
| Chloride c                  | T3 free f (reflex only)                       |
| Creatinine d                | T4 free f (reflex only)                       |
| Gamma glutamyltransferase c | Urea or blood urea nitrogen, depending on local practice |
| Glucose                                |  |
| Lactate dehydrogenase                  |  |

- 
- a Tests for ALT, AST, alkaline phosphatase, and total bilirubin must be conducted and assessed concurrently. If total bilirubin is  $\geq 2 \times$  upper limit of normal (and no evidence of Gilbert's syndrome), then fractionate into direct and indirect bilirubin.
- b It is preferable that both amylase and lipase parameters are assessed. For sites where only 1 of these parameters is routinely measured, either lipase or amylase is acceptable.
- c Bicarbonate (where available), chloride, creatinine clearance, gamma glutamyltransferase, magnesium, testing are to be performed at baseline, on Day 1 (unless all screening laboratory clinical chemistry assessments are performed within 3 days prior to Day 1), and if clinically indicated.
- d Creatinine clearance will be calculated by data management using Cockcroft-Gault (using actual body weight).
- e If TSH is measured within 14 days prior to Day 1 (first infusion day), it does not need to be repeated at Day 1.
- f Free T3 or free T4 will only be measured if TSH is abnormal or if there is a clinical suspicion of an AE related to the endocrine system.
- ALT Alanine aminotransferase; AST Aspartate aminotransferase, TSH Thyroid-stimulating hormone.

**Table 4 Hematology**

---

|  |  |
|--|--|
| Absolute neutrophil count a | Absolute lymphocyte count a |
| Hemoglobin                             | Platelet count                         |
| Total white cell count                 |  |

---

- a Can be recorded as absolute counts or as percentages. Absolute counts will be calculated by Data Management if entered as percentage. Total white cell count therefore has to be provided.

**Table 5**            **Urinalysis**

---

|                      |                  |
|----------------------|------------------|
| Bilirubin            | Ketones          |
| Blood                | pH               |
| Color and appearance | Protein          |
| Glucose              | Specific gravity |

---

Note: Urinalysis should be done at baseline (screening) and then as clinically indicated.

Note: Microscopy is preferred to investigate white blood cells, with use of high power field for red and white blood cells; dipstick can be used as well.

If a patient shows an AST or ALT  $\geq 3 \times$  ULN together with total bilirubin  $\geq 2 \times$  ULN, refer to Appendix B for further instructions on cases of increases in liver biochemistry and evaluation of Hy's Law. These cases should be reported as SAEs if, after evaluation, they meet the criteria for a Hy's law case or if any of the individual liver test parameters fulfill any of the SAE criteria.

Any clinically significant abnormal laboratory values should be repeated as clinically indicated and recorded on the eCRF. Situations in which laboratory safety results should be reported as AEs are described in Section 7.3.6.

All patients with Grade 3 or 4 laboratory values at the time of completion or discontinuation from IP must have further tests performed until the laboratory values have returned to Grade 1 or 2, unless these values are not likely to improve because of the underlying disease.

### **6.3.2**            **Physical examinations**

At screening and each visit during the treatment period, a complete physical examination will be performed and include an assessment of the following: general appearance, respiratory, cardiovascular, abdomen, skin, head and neck (including ears, eyes, nose and throat), lymph nodes, thyroid, musculo-skeletal (including spine and extremities) and neurological systems.

Physical examination information will only be reported in the CRF if abnormalities are reported as AEs.

### **6.3.3**            **Vital signs**

Vital signs will be monitored at screening and at every visit during the study. During durvalumab infusions, vital signs should be monitored as per institutional care recommendations for the administration of monoclonal antibodies. Vital signs will be reported if abnormalities are reported as AEs.

### **6.3.4 Electrocardiograms**

Resting 12-lead ECGs will be recorded at screening and as clinically indicated throughout the study (see the SoAs). ECGs should be obtained after the patient has been in a supine position for 5 minutes and recorded while the patient remains in that position.

In case of clinically significant ECG abnormalities, including a QTcF value >470 ms, 2 additional 12-lead ECGs should be obtained over a brief period (eg, 30 minutes) to confirm the finding.

### **6.3.5 WHO/ECOG performance status**

WHO/ECOG performance status will be assessed at the times specified in the assessment schedules (see the SoAs) based on the following:

0. Fully active; able to carry out all usual activities without restrictions
1. Restricted in strenuous activity, but ambulatory and able to carry out light work or work of a sedentary nature (eg, light housework or office work)
2. Ambulatory and capable of self-care, but unable to carry out any work activities; up and about more than 50% of waking hours.
3. Capable of only limited self-care; confined to bed or chair more than 50% of waking hours
4. Completely disabled; unable to carry out any self-care and totally confined to bed or chair
5. Dead

*Any significant change from baseline or screening must be reported as an AE.*

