## **7 SAFETY REPORTING AND MEDICAL MANAGEMENT**

### **7.1 Definition of adverse events**

An AE is the development of an undesirable medical condition (other than progression of the malignancy under evaluation) or the deterioration of a pre-existing medical condition following or during exposure to a pharmaceutical product, whether or not considered causally related to the product. An undesirable medical condition can be symptoms (eg, nausea, chest pain), signs (eg, tachycardia, enlarged liver), or the abnormal results of an investigation (eg,

laboratory findings). In clinical studies, an AE can include an undesirable medical condition occurring at any time, including run-in or washout periods, even if no study treatment has been administered.

The term AE is used to include both SAEs and non-serious AEs.

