### **7.3.3 Adverse event data collection**

The following variables will be collected for each AE:

- AE (verbatim)
- The date when the AE started and stopped
- The maximum CTCAE grade reported
- Changes in CTCAE grade (report only the maximum CTCAE grade for a calendar day)
- Whether the AE is serious or not
- Investigator causality rating against the IPs (yes or no)
- Action taken with regard to IPs
- Administration of treatment for the AE
- Outcome

In addition, the following variables will be collected for SAEs:

- Date the AE met criteria for SAE
- Date the Investigator became aware of the SAE
- Seriousness criteria
- Date of hospitalization
- Date of discharge
- Probable cause of death
- Date of death
- Whether an autopsy was performed
- Causality assessment in relation to study procedure(s)
- Causality assessment in relation to other medication, as explained in Section 7.3.4
- Description of the SAE

The grading scales found in the revised NCI CTCAE version 5.0 will be utilized for all events with an assigned CTCAE grading. For those events without assigned CTCAE grades, the recommendation in the CTCAE criteria that converts mild, moderate, and severe events into CTCAE grades should be used. A copy of the CTCAE version 5.0 can be downloaded from the Cancer Therapy Evaluation Program website (<http://ctep.cancer.gov>).

It is important to distinguish between SAEs and severe AEs. Severity is a measure of intensity, whereas seriousness is defined by the criteria in Section 7.2. An AE of severe intensity need not necessarily be considered serious. For example, nausea that persists for several hours may be considered severe nausea, but it is not an SAE unless it meets the criteria shown in Section 7.2. On the other hand, a stroke that results in only a limited degree of disability may be considered a mild stroke, but it would be an SAE if it satisfies the criteria shown in Section 7.2.

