#### **7.3.6 Adverse events based on examinations and tests**

Deterioration as compared to baseline in protocol-mandated laboratory values should only be reported as AEs if they fulfil any of the SAE criteria or are the reason for discontinuation of treatment with the investigational product.

If deterioration in a laboratory value/vital sign is associated with clinical signs and symptoms, the sign or symptom will be reported as an AE and the associated laboratory result/vital sign will be considered as additional information. Wherever possible the reporting Investigator uses the clinical, rather than the laboratory term (eg, anemia versus low hemoglobin value). In the absence of clinical signs or symptoms, clinically relevant deteriorations in non-mandated parameters should be reported as AE(s).

Deterioration of a laboratory value, which is unequivocally due to disease progression, should not be reported as an AE/SAE.

Any new or aggravated clinically relevant abnormal medical finding at a physical examination as compared with the baseline assessment will be reported as an AE unless unequivocally related to the disease under study.

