### **7.3.8 Disease-under-study (DUS)**

Symptoms of DUS are those which might be expected to occur as a direct result of extensive-stage small cell lung cancer. Events which are unequivocally due to disease under study should not be reported as an AE during the study unless they meet SAE criteria or lead to discontinuation of the investigational product.

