### **7.3.9 Disease progression**

Disease progression can be considered as a worsening of a patient's condition attributable to the disease. It may be an increase in the severity of the disease under study and/or increases in the symptoms of the disease. The development of new, or progression of existing metastasis to the primary cancer under study should be considered as disease progression and not an AE. Events, which are unequivocally due to disease progression, should not be reported as an AE during the study.

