### **7.3.11 Deaths**

All deaths that occur during the study treatment period, or within the protocol-defined follow-up period after the administration of the last dose of study drug, must be reported as follows:

- Death clearly resulting from disease progression should be reported to the Study Monitor/Physician at the next monitoring visit and should be documented. It should not be reported as an SAE.
- Where death is not due (or not clearly due) to progression of the disease under study, the AE causing the death must be reported to the Study Monitor/Physician as an SAE within 24 hours. It should also be documented in the Statement of Death page in the eCRF. The report should contain a comment regarding the co involvement of PD, if appropriate, and should assign main and contributory causes of death.

- Deaths with an unknown cause should always be reported as an SAE. It should also be documented in the Statement of Death page. A post mortem may be helpful in the assessment of the cause of death, and if performed, a copy of the post-mortem results should be forwarded to AstraZeneca Patient Safety or its representative within the usual timeframes.

Deaths occurring after the protocol defined safety follow up period after the administration of the last dose of study drug should be documented in the Statement of Death page. If the death occurred as a result of an event that started post the defined safety follow up period and the event is considered to be due to a late onset toxicity to study drug then it should also be reported as an SAE.

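### Section 6.3.5 makes every significant ECOG change an AE with no disease exception, against Sections 7.3.8 and 7.3.9, so tumour-related decline can enter the primary Grade ≥3 AE incidence

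*Protocol*

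**What the plan says.** Four places in the protocol govern whether a tumour-related decline in function is an AE.

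- Section 6.3.5, after the ECOG scale: "Any significant change from baseline or screening must be reported as an AE". It does not define a significant change, carries no exception and refers to no other section.
- Section 7.3.9: "Events, which are unequivocally due to disease progression, should not be reported as an AE during the study". It has no exception. It also treats an increase in the symptoms of the disease as progression.
- Section 7.3.8: events unequivocally due to the disease "should not be reported as an AE during the study unless they meet SAE criteria or lead to discontinuation of the investigational product".
- Section 7.3.6, on physical examination: a new or worse finding "will be reported as an AE unless unequivocally related to the disease under study". It also exempts laboratory deterioration that is unequivocally due to progression.

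The general definition in Section 7.1 reads: "An AE is the development of an undesirable medical condition (other than progression of the malignancy under evaluation"), and goes on to include deterioration of a pre-existing condition. Section 7.3.11 says of a death clearly resulting from progression: "It should not be reported as an SAE".

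The link to the primary analysis runs through four further places. Table 2 schedules ECOG at screening, baseline, the treatment visits and the 90-day safety visit. Section 7.3.3 covers grading where no grade is assigned: "For those events without assigned CTCAE grades, the recommendation in the CTCAE criteria that converts mild, moderate, and severe events into CTCAE grades" is to be used. Section 9.4.1 includes AEs in the summaries until 90 days after durvalumab stops. Section 9.5.1 makes the percentage of patients with a Grade ≥3 AE, from any cause, a primary outcome.

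**The concern.** Sections 7.1, 7.3.6, 7.3.8, 7.3.9 and 7.3.11 all aim to keep tumour outcome out of the toxicity record. Section 6.3.5 does not follow them. Two sites with the same patient could record differently, each able to cite the protocol.

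What is at stake is what the primary estimate counts. The Grade ≥3 incidence is all-cause, and the study has a single arm, so no control group carries the same error. The counting window runs 90 days past the last durvalumab dose and so covers the time around progression, when function is likely to fall. The confidence interval does not reflect this source of error.

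A second inconsistency affects the SAE and discontinuation-AE counts, which are secondary endpoints. A symptom of progressing disease that is serious or stops treatment is reportable under 7.3.8 and barred under 7.3.9. Stopping treatment for clinical progression is an expected event under Section 4.6, so this is not a rare case.

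**Working it through.** **The rules side by side.** Take a patient at PS 1 with documented progression who falls to PS 3, where the cause is unequivocally the tumour.

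| Rule | Neither serious nor treatment-stopping | Serious or treatment-stopping |
|---|---|---|
| 6.3.5 | AE required | AE required |
| 7.3.8 | AE barred | AE reportable |
| 7.3.9 | AE barred | AE barred |

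The left column is the conflict between 6.3.5 and both disease rules. The right column adds the conflict between 7.3.8 and 7.3.9. A decline whose cause is unclear falls outside both disease rules and is not in dispute.

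**Steps needed to affect the primary incidence.** All must hold: (a) the decline is unequivocally disease-related; (b) the site records it under 6.3.5; (c) it falls within the summary window; (d) it is graded 3 or higher; (e) the patient has no other Grade ≥3 AE. The protocol links no ECOG level to a CTCAE grade, so (d) is possible but not stated.

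**The plan's own figure.** Section 9.2 gives n = 300, incidence 60% and precision 5.7% by Clopper-Pearson. With x = 180:

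- lower limit = 0.025 quantile of Beta(x, n − x + 1) = Beta(180, 121): 54.21%
- upper limit = 0.975 quantile of Beta(x + 1, n − x) = Beta(181, 120): 65.59%
- half-width = (65.59 − 54.21)/2 = 5.69 points

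This agrees with the stated 5.7. The other cells of Table 9 also reproduce to one decimal. The precision arithmetic is sound.

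**Size of the shift.** Let k be the number of patients counted only because of a disease-related ECOG decline. The shift is k/300, or 100/300 = 0.33 points per patient. At 60% incidence, 300 − 180 = 120 patients have no other Grade ≥3 AE, and k comes from these. The values of k are assumed.

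| k | Share of the 120 | Incidence | 95% CI | Shift (points) |
|---|---|---|---|---|
| 0 | 0% | 180/300 = 60.0% | 54.21 to 65.59 | 0 |
| 6 | 5% | 186/300 = 62.0% | 56.24 to 67.52 | 2.0 |
| 12 | 10% | 192/300 = 64.0% | 58.28 to 69.44 | 4.0 |
| 18 | 15% | 198/300 = 66.0% | 60.33 to 71.35 | 6.0 |

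At k = 17 the shift is 17/300 = 5.67 points, just inside the planned half-width. At k = 18 it exceeds it, and the interval excludes the 60% that would have been seen without these patients.

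**The case against.** The best defence is that AE is a defined term. Section 7.1 excludes progression of the malignancy, and 7.3.8 and 7.3.9 are the specific attribution rules, so the sentence in 6.3.5 should be read subject to them. On that view only a cross-reference is missing. This has force, but it does not settle the matter. Section 7.1 excludes progression itself and does not clearly exclude the functional decline that follows from it. The sentence in 6.3.5 is worded as an absolute duty, and 7.3.6 shows that the protocol writes the exception out where it wants one.

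Several limits on size do stand. The clash covers only unequivocal cases. Section 7.3.5 prefers a diagnosis to a sign or symptom, which should reduce entries made simply as a performance-status change. Section 9.5.1 summarises Grade ≥3 AEs by preferred term and by relationship to treatment and lists them by patient, so such entries could be found.

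A reader might go further in ways the documents do not support.

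- Improvement in ECOG is not made an AE: Section 7.1 requires an undesirable condition. The scale's label for death adds nothing either, since 7.3.11 governs deaths.
- The 12-month progression-free rate of 17.5% cannot be used to project the number affected. In Section 2.2.1.2 it is the result of the cited phase III trial, not a planning figure for this study. This protocol's own figure is about 60% PFS maturity at the primary analysis. Neither yields a rate of Grade ≥3 ECOG events without a further share that has no source.
- Variation between sites, and a larger effect in PS 2 patients, are reasonable inferences, but the document gives nothing to quantify them.

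**Conclusion.** The contradiction is in the current text and holds as a point of wording: an ECOG decline unequivocally due to the tumour is required as an AE by 6.3.5 and prohibited by 7.3.9, and by 7.3.8 unless it is serious or stops treatment. It can reach the primary Grade ≥3 incidence. How far it does so is unknown. The 2 to 6 point range rests wholly on the assumption that 6 to 18 of 300 patients are counted for this reason alone, with 60% as the underlying incidence. Only the upper end of that range exceeds the planned precision.

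The overlap between 7.3.8 and 7.3.9 is a separate inconsistency, to be resolved in its own right. Overall this is a should-fix: certain as to the conflict, moderate confidence as to its impact.

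**What to change.** 1. Amend the sentence in 6.3.5 along these lines: *A clinically significant worsening of performance status from baseline is recorded as an AE, except where it is unequivocally caused by the disease under study or its progression; for those cases see Sections 7.3.8 and 7.3.9.* This limits the rule to worsening and matches the exception in 7.3.6. It would help to state what counts as clinically significant.
2. List the AEs already entered as a performance-status change and query the sites on attribution under the amended rule. The investigator should make the attribution and the change should be documented, because these records feed a primary endpoint in an open-label study.
3. Separately, reconcile 7.3.8 with 7.3.9 for symptoms of progressing disease that are serious or stop treatment, and state explicitly how serious events are handled. Merging the two sections without that statement could remove SAE reporting by default.

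The cost is a wording change in three short sections, a note to sites and one query listing. No new data are needed. The reported Grade ≥3 incidence may come out lower, so the number of records changed by the query should be reported with it.
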